#### **4.11.6 Fenofibrate and renal function**

It is well established that fenofibrate therapy increases creatinine, that this effect is exerted quickly and that it is fully reversible. British National Formulary (BNF) advice is to use a lower dose at eGFR 20-59mL/min/1.73m^2 (namely 134mg/d), a further reduced dose at eGFR 15-19mL/min/1.73m^2 (67mg/d) and to stop treatment below eGFR 15mL/min/1.73m^2. Notably, there is no evidence that those with the greatest increase in creatinine on fenofibrate experience any clinical disadvantage, the reduction in urine albumin on the drug suggests the possibility of renal benefit, and fenofibrate treatment actually slows the rate of the fall in eGFR over time. In addition, there is evidence of potential cardiovascular benefit in patients with chronic kidney disease who are treated with fenofibrate. Renal function will be checked at screening and after approximately eight weeks' open-label run-in treatment, providing information on safety. Thereafter, monitoring of renal function in LENS will be based on results from blood samples taken as part of routine clinical practice. Scottish Diabetes Survey data indicate that 94% with DM have renal function checked every 15 months. Both the eGFR thresholds and doses used in the trial are also more conservative than what is recommended in the BNF. In addition, participants can attend the LCC for a blood test to confirm their renal function status if there is any clinical concern over their continuation on allocated study drug. All biochemistry laboratories in NHS Scotland report both serum creatinine and eGFR.

#### **4.11.7 Dosage modifications**

Participants whose Randomisation visit eGFR (i.e. after open-label treatment with fenofibrate) is  $\geq 60\text{mL/min}/1.73\text{m}^2$  and whose eGFR falls to  $30\text{--}59\text{mL/min}/1.73\text{m}^2$  thereafter while on randomised study treatment will be required to reduce study drug to one tablet every second day (see section 4.6.3). The local PI or clinician with delegated responsibility or experienced CCO clinician will be required to electronically sign an updated 'order to supply' to verify this. Participants whose eGFR falls below  $30\text{mL/min}/1.73\text{m}^2$  will be asked to discontinue study drug therapy (see section 4.6.3). Dosage will not be reduced based on patient request alone. Participants who experience a transient worsening in renal function due to a self-limiting illness (e.g. gastro-enteritis) during which study treatment has been stopped will be able to restart study medication in accordance with their renal function.

#### **4.11.8 Plan for study treatment after the occurrence of a pre-specified outcome**

Participants should keep taking allocated study treatment if a primary, secondary or tertiary outcome occurs unless any contra-indication has developed or if a doctor responsible for their care wishes to prescribe a fibrate.

#### **4.11.9 Contra-indications**

Exclusion criteria of the trial are in accordance with the SmPC which lists the following conditions as contra-indications – hepatic insufficiency (including biliary cirrhosis), renal insufficiency, children, hypersensitivity to fenofibrate or any component of this medication, known photo-allergy or phototoxic reaction during treatment with fibrates or ketoprofen, gallbladder disease, chronic or acute pancreatitis; no suitable data regarding use in pregnancy and/or lactation exist.

#### **4.11.10 Concomitant medications and potential interaction with other therapies**

If a participant commences any fibrate, vitamin K antagonist therapy (warfarin, acenocoumarol or phenindione), cyclosporin (an immunosuppressant), colchicine (gout medication), ketoprofen (NSAID), daptomycin (antibiotic) or rosuvastatin (only 40mg daily) therapy during LENS, they will need to discontinue fenofibrate but they will remain under active follow-up. Participants will be asked about such therapies during post-baseline questionnaires. If such a treatment is subsequently discontinued at any later point in the trial, the participant will be asked by the research team for their permission to recommence study treatment. A post hoc analysis of the ACCORD-Lipid trial found that a greater number of participants allocated to fenofibrate developed a low HDL-cholesterol level compared to placebo recipients (5% absolute excess) and that this was limited to participants receiving a glitazone. It has not been demonstrated that this biochemical finding increases clinical risk. It is anticipated that only approximately 8% (n=80) of LENS participants are likely to be treated with a glitazone indicating that this effect, if true, should only occur in fewer than five participants on fenofibrate. The numbers of participants who have developed a HDL-cholesterol level  $\leq 0.60\text{mmol/L}$  will be reported to the DMC at approximately one year after the completion of randomisation.

#### **4.11.11 Concomitant statin therapy**

Many adult patients with DM in Scotland are already on statin therapy. Combination therapy consisting of gemfibrozil and statins is contraindicated based on an increased risk of rhabdomyolysis. This led to previous concerns about a fenofibrate-statin combination however there is nowadays widespread clinical use of the combination of statins and fenofibrate. The ACCORD-Lipid trial, a double-blinded RCT comparing fenofibrate plus simvastatin to simvastatin plus placebo in 5,518 patients with type 2 DM, found no increased rates of any serious side-effects including muscle-related side-effects, whether defined in terms of reports of muscle pain, recorded

SAEs (myopathy or myositis) or increases in CK levels to >5X or >10X normal among those on statin plus fibrate versus statin alone. In ACCORD-Lipid, the number of participants developing elevated ALT was: ALT >3X ULN 52 (1.9%) vs. 40 (1.5%) cases (non-significant) and for ALT >5X ULN 16 (0.6%) vs. 6 (0.2%) cases (borderline significant; ALT >3X ULN includes these 22 cases with ALT >5X ULN). Systematic reviews of the effects of fenofibrate on a variety of possible side-effects show no increased rate of side-effects on the combination of statin and fenofibrate. Fenofibrate also does not affect the pharmacokinetics of simvastatin or atorvastatin. The safety of combination therapy with a statin is underlined by the UK's licensing which allows the use of fenofibrate as an adjunct to statin therapy in certain groups of patients, as well as by the availability of preparations containing both fenofibrate and simvastatin. However, based on regulatory feedback, patients taking rosuvastatin 40mg daily will be excluded from the trial and any participant who commences rosuvastatin 40mg daily during follow up will be required to discontinue study treatment.

#### **4.11.12 Trial restrictions**

There are no dietary or lifestyle restrictions during the trial.

Female participants of child-bearing potential must be using adequate contraception for the duration of the trial and for at least 7 days after discontinuing the study drug, whether due to the end of the trial or withdrawal. Adequate contraception includes:

- Intrauterine Device
- Hormonal based contraception (pill, contraceptive injection etc.)
- Double Barrier contraception (condom and occlusive cap e.g. diaphragm or cervical cap with spermicide)
- True abstinence: when this is in line with the preferred and usual lifestyle of the subject

#### **4.11.13 Assessment of compliance**

Compliance with open-label active run-in fenofibrate will be assessed at the randomisation visit. Thereafter, randomised participants will be asked about their compliance to treatment in six monthly trial-specific questionnaires.

#### **4.11.14 Drug mail-out**

As noted above, LENS study medication will be sent to participants by routine post, namely by Royal Mail which is the only provider obliged to provide coverage to the whole of mainland Scotland. Other ongoing or recently completed randomised trials in cardiovascular disease in the UK such as ASCEND (<https://ascend.medsci.ox.ac.uk>; n=15,000 randomised to aspirin or placebo; run by CTSU), FAST (<http://www.fast-study.co.uk>; n=5,700 to assess the cardiovascular safety of feboxustat) and GLINT (<https://www.dtu.ox.ac.uk/GLINT/>; n=250 randomised to metformin or placebo; jointly run by the Diabetes Trials Unit, University of Oxford) have also sent study medication by routine post. Various steps will be taken to ensure the reliability of this method of delivery and these are described in the relevant parts of the protocol. These steps include: (i) phone calls by LCC nurses during run-in to verify receipt of study medication and to collect and record the study medication verification code (ii) automated texts/emails in parallel with study medication mail-out to inform participants that their study medication is en route and requesting that they contact the CCO if it is not received (iii) asking about receipt of study medication plus, where possible, study medication verification codes as part of six monthly trial-specific follow-up questionnaires. In addition, LENS participants will have access to an experienced CCO clinician via the CTSU Freephone number at any time.

## 5 PHARMACOVIGILANCE

### 5.1 DEFINITIONS TO BE USED IN LENS

**Table 5.** AE definitions to be used in LENS

Term	Definition
Adverse Event (AE)	Any untoward medical occurrence in a participant to whom a medicinal product has been administered, including occurrences which are not necessarily caused by or related to that product.
Adverse Reaction (AR)	An untoward and unintended response in a participant to an investigational medicinal product (IMP) which is related to any dose administered to that participant
Serious Adverse Event (SAE)	A SAE is any untoward medical occurrence that: 
 
• results in death
 
• is life-threatening
 
• requires unplanned inpatient hospitalisation (excluding A&E attendances without admission to a hospital ward) or prolongation of existing hospitalisation
 
• results in persistent or significant disability/incapacity
 
• consists of a congenital anomaly or birth defect
 
 Other 'important medical events' may also be considered serious if they jeopardise the participant or require an intervention to prevent one of the above consequences.
Suspected Serious Adverse Reaction (SSAR)	An AE that is both serious and, in the opinion of the reporting Investigator or clinician, believed with reasonable probability to be caused by the trial treatment, based on the information provided.
Suspected Unexpected Serious Adverse Reaction (SUSAR)	A serious AR, the nature and severity of which is not consistent with the information about the medicinal product in question set out in the SmPC.
Overdose	Any occasion in which a member of the research team learns that a participant has taken at least 6 study tablets within a 24 hour period

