### 4.11.3 Summary of Product Characteristics (SmPC)

The relevant section of the SmPC for fenofibrate will be used as the Reference Safety Information during the trial for pharmacovigilance reporting purposes. The sponsor will periodically check (at least once a year) for any changes to the licensing status of fenofibrate.

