### 5.3.2 SSARs

Any SAE that is considered, with a reasonable probability, to be due to study treatment is potentially a SSAR. In making this assessment there should be consideration, based on:

- the available information,
- the probability of an alternative cause
- the timing of the reaction with respect to study treatment
- the response to withdrawal of the study treatment
- the response to subsequent re-challenge (where appropriate)

Any potential SSAR which comes to the attention of LCC staff must be reported to the CCO immediately (at least within 24 hours) of becoming aware of it. The following standard information will be obtained and recorded:

- Participant study number
- Identity of reporting person
- Event description
- Reason for attribution to study treatment

All such SSAR reports will be reviewed urgently by the Chief Investigator (or delegated deputy) at the CCO, who will assess the evidence for seriousness and relatedness, seek any additional information required (including relevant information relating to medical history and treatment both prior to and following randomisation), and assess expectedness based on the SmPC.

Any SSAR that is considered to be "unexpected" (i.e. a Suspected Unexpected Serious Adverse Reaction [SUSAR]) will lead to the relevant participant being unblinded. All SUSARs for participants randomized to active fenofibrate will be reported by the CCO to the MHRA and REC in an expedited fashion. For SUSARs that are fatal or life-threatening, an initial report will be submitted within 7 days (*7 day report*) of the date received, with a follow-up report provided within 8 days of the initial report, if required. For all other SUSARs, a 15 day report will be required. The following minimum information will be required for any SUSAR report:

- EudraCT number for the trial (2016-002656-24)
- Name of the suspected study medication (fenofibrate)
- Participant study number
- Identity of reporting person

---

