 As recommended by regulatory authorities, a Suspected Serious Adverse reaction (SSAR) should be considered an unanticipated problem requiring expedited reporting only if it is either an event that is uncommon and strongly associated with drug exposure (such as angioedema, agranulocytosis, hepatic injury, or Stevens-Johnson syndrome), or an event that is not commonly associated with drug exposure, but uncommon in the study population (e.g. tendon rupture, progressive multifocal leukoencephalopathy).

- Event description
- Reason for attribution to study treatment
- Treatment assignment after unblinding

Confirmed reports of SSARs and SUSARs will be promptly forwarded to the chairman of the Data Monitoring Committee (DMC) and will be included in the Development Safety Update Report (DSUR) sent to the REC and MHRA. Study treatment will be discontinued in the event of a confirmed SSAR or SUSAR. Local PIs will be informed of any SUSARs which occur during LENS.

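### Footnote 1 to Protocol 5.3.2 excludes from expedited reporting some SUSARs that the body of the same section requires to be expedited

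*Protocol*

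**What the plan says.** The main text of the protocol builds one rule across four places.

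- Section 4.11.3: the relevant section of the SmPC "will be used as the Reference Safety Information during the trial for pharmacovigilance reporting purposes".
- Table 5 in section 5.1: a SUSAR is a serious adverse reaction, "the nature and severity of which is not consistent with the information about the medicinal product in question set out in the SmPC". The definition has no frequency condition.
- Section 5.3.2, body: the Chief Investigator or a deputy is to "assess expectedness based on the SmPC". Then: "All SUSARs for participants randomized to active fenofibrate will be reported by the CCO to the MHRA and REC in an expedited fashion". Fatal or life-threatening SUSARs get a first report within 7 days. "For all other SUSARs, a 15 day report will be required".
- Section 5.5.3: expedited reporting of SUSARs is listed as a duty of the CCO, with no further filter.

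Footnote 1 to section 5.3.2 adds something different. Its marker is on the sentence "Any SAE that is considered, with a reasonable probability, to be due to study treatment is potentially a SSAR". Its text, presented as a recommendation of regulatory authorities, sets a test for any SSAR: it "should be considered an unanticipated problem requiring expedited reporting only if it is either an event that is uncommon and strongly associated with drug exposure". After some examples, the second limb of the test reads: "or an event that is not commonly associated with drug exposure, but uncommon in the study population". The footnote does not refer to the SmPC, to expectedness or to the term SUSAR.

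**The concern.** Two tests for the same reporting duty sit in one section, and they use different criteria. The body asks whether the reaction is consistent with the SmPC. The footnote asks how common the event is and how closely it is tied to drug exposure. Nothing says which prevails or whether both must be met.

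An assessor who follows the footnote could hold back a 7- or 15-day report that the body text requires. The reactions exposed to this are those not consistent with the SmPC that resemble illness already seen in adults with diabetes.

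More than one person makes these judgements. Relatedness may be decided by an LCC or a CCO doctor (5.3.1), and the Chief Investigator's review may be delegated (5.3.2, 5.5.2). Whether a given reaction is expedited could therefore depend on which sentence the assessor relied on.

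**Working it through.** No arithmetic applies. The check is to write both rules as conditions and see where they give opposite answers.

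**Body rule** (Table 5, 4.11.3, 5.3.2, 5.5.3). Expedite if the event is serious, suspected to be related, not consistent with the SmPC, and in a participant randomised to active fenofibrate. The 7-day category and the 15-day category together cover all such SUSARs, so none is exempt.

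**Footnote rule** (5.3.2, footnote 1). Expedite only if limb (a) or limb (b) is met.
- Limb (a): the event is uncommon and strongly associated with drug exposure.
- Limb (b): the event is not commonly associated with drug exposure and is uncommon in the study population.

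Uncommonness is needed in both limbs. *Only if* makes this a necessary condition: meeting a limb permits expedited reporting but does not by itself require it.

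Take a serious event, judged related, in a participant randomised to fenofibrate:

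| Case | Body rule | Footnote 1 | Conflict? |
|---|---|---|---|
| A. Not consistent with SmPC; meets a limb | Expedite | Permitted | No |
| B. Not consistent with SmPC; not uncommon | Expedite | Excluded | **Yes** |
| C. Consistent with SmPC; uncommon and strongly drug-associated | Do not expedite | Permitted, not required | No |
| D. Consistent with SmPC; not uncommon | Do not expedite | Excluded | No |

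Only case B gives opposite answers. Limb (a) does not say in which population the event must be uncommon. I read it as the study population, as limb (b) states. An event that is not uncommon on any reading fails both limbs regardless.

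The next step is to see what else depends on the footnote.

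- **Unblinding.** Section 5.3.2 ties it to the SSAR being unexpected. The footnote does not address expectedness, so unblinding is unaffected.
- **DMC and DSUR.** Confirmed SSARs and SUSARs both go promptly to the DMC chair and into the DSUR sent to the REC and MHRA. An event excluded by the footnote is still a SSAR, so both routes remain.
- **DMC tabulations.** Section 5.3.1 gives the DMC unblinded tabulations of all SAEs, with no rarity condition.
- **Expedited report to the MHRA and REC.** This is the only step that the footnote's condition governs.

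**The case against.** The strongest reply is that the footnote is guidance on attribution and was never meant as a reporting filter. Its marker is on the causality sentence, directly before the list of factors for judging causality. It speaks of an unanticipated problem, a term that Table 5 does not define, and every other relevant section gives the SmPC rule consistently. This is a plausible account of the intent. It does not remove the conflict, because the footnote starts from an event that is already a SSAR and then says when that event requires expedited reporting. If causality guidance was meant, the words do not say so.

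A second reply is that the disputed class is small. An event common in this population will often be put down to an alternative cause, and so fail the causality step before either reporting rule applies. That is fair, and it limits the practical reach. It does not empty the class, since some such events may still be judged related.

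Two objections to wider readings stand in full.

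- A reader might infer that the rules also clash for a rare, strongly drug-associated reaction already listed in the SmPC. They do not (case C): the footnote permits expedited reporting there but does not demand it. At most it could be misread.
- A reader might offer a cardiovascular event as a concrete instance of case B. That depends on what the SmPC lists, and its list of effects is not in the documents. The argument does not need the example.

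**Conclusion.** The inconsistency is real and one-way. For a suspected serious reaction that is not consistent with the SmPC and not uncommon in this population, in a participant randomised to fenofibrate, the body of 5.3.2 requires an expedited report and footnote 1 rules it out. Table 5 itself is sound; the text that does not fit is the footnote.

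The consequence is limited to expedited reporting. A reader might infer that such reactions would go unreported or that participants would not be unblinded. The documents do not support either: notice to the DMC chair and DSUR inclusion continue, and unblinding follows expectedness.

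The frequency cannot be derived. The documents give no threshold for uncommon, no SmPC list and no expected rate of suspected serious reactions. The body rule covers those randomised to fenofibrate, approximately 530 of at least 1,060. It would be wrong to take everyone exposed in the active run-in as the population affected. No endpoint, analysis or sample size is involved.

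The conclusion rests on a literal reading of *only if* and on the absence of any statement ranking the two rules. It is worth correcting because the footnote, if followed, would withhold expedited reports that the protocol elsewhere requires.

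**What to change.** Reconcile the two texts at the next amendment. Either delete the conditional sentence in footnote 1, or reword it as guidance on judging whether an event is caused by study treatment, with no mention of expedited reporting.

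In either case, state in 5.3.2 that expedited reporting follows the body rule alone: serious, suspected to be related, not consistent with the SmPC, and in a participant randomised to active fenofibrate. The last condition should be written out. A pointer to the Table 5 definition alone would drop it without notice.

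The cost is one footnote and one sentence. No data collection or analysis changes. The only downside is possibly a few more expedited reports.

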### 5.2 EVENTS ASSOCIATED WITH FENOFIBRATE USE

The most commonly reported AEs during fenofibrate therapy are digestive, gastric or intestinal disorders. The SmPC provides a list of the undesirable effects that have been observed during placebo-controlled clinical trials and post-marketing studies. The SmPC will be reviewed at least annually for changes.

## 5.3 RECORDING AND REPORTING ADVERSE EVENTS

Fenofibrate is a well profiled medicine which has been studied intensively in major cardiovascular trials of over 15,000 participants and it is also licensed to treat patients with dyslipidaemia. In 2016, NHS Scotland data show that 18,600 NHS prescriptions were issued for fenofibrate (and 27,000 prescriptions for the closely related bezafibrate).

### 5.3.1 NSAEs and SAEs

Participants in LENS are not considered to be at higher risk of ARs than these groups. Information regarding the occurrence of non-serious AEs in this streamlined mail-based trial will therefore not be systematically collected unless they are medical eye procedures or they lead to the cessation of study treatment. Other reasons for cessation of study treatment will also be collected. Information on all SAEs will be collected and reported. The information that will be collected for AEs is:

- description of event
- seriousness
- date of onset
- end date (if resolved)
- an assessment of the relationship between study treatment and the AE (i.e. relatedness)

With the exception of AEs identified by registry linkage, where no assessment of relatedness is possible, relatedness will be determined by the LCC doctor and/or CCO doctor.

Information regarding AEs will be collected from the following sources:

- six monthly trial-specific questionnaires (by telephone or, where necessary, medical records)
- electronic linkage to health registry data and death records
- 24hr Freephone service
- manual searches of electronic health records
- LCC staff

Participants will have a card with details of the trial, CCO contact information and the Freephone number to facilitate reporting of any events. Data for AEs will be collected from the point of screening an individual up until the final registry linkages and questionnaires are completed.

SAEs brought to the attention of the LCC, whether during phone questionnaires or by ad hoc reports, will be reported to the Sponsor immediately (within 24 hours) of trial staff becoming aware of them. Such SAEs, and any SAEs reported via Freephone to the CCO, will be recorded in the trial's web-based CRF immediately. Reporting of SSARs is discussed in the next section.

Verification of all SAEs will not be sought from health records with the following important exceptions:

- possible cardiovascular events
- possible lower limb amputations
- SSARs (including SUSARs)

Information regarding SAEs provided in trial-specific questionnaires will be assumed to be correct unless refuted by information from the participant's health records or health registry linkage. The CCO may request further information where information regarding a SAE is considered incomplete.

Procedures for verification and adjudication of potential study endpoints are described in section 3.3.

Experienced doctors within the CCO will review the blinded listing of all AEs on a regular basis (approximately daily). Tabulations of all SAEs and reasons for stopping study treatment will be provided to the DMC (unblinded) and the TSC (blinded) in the relevant reports. Information regarding AEs will be reported to Mylan in accordance with the legal agreement between the University of Oxford and Mylan.

